8.7.4 Physical examinations

An abbreviated physical examination (PE) will be conducted at the screening visit and Day -1. Symptom-directed PEs will be performed at all other subsequent visits. Any new findings on PE post dosing or worsening of existing conditions will be reported as AEs, which will be summarized descriptively by treatment group using frequencies and percentages. Subjects with documented AEs based on PEs will be identified using listings and summarized by treatment group and study day. Abnormal physical exams will be summarized by treatment group.

8.7.5 Electrocardiograms

12-lead ECG will be performed at screening and on dosing day (30±10 minutes after injection) while subject is in supine position using an ECG machine that automatically calculates the heart rate and measures PR, QRS, and QT (QTcF), intervals. Results will be categorized as normal sinus rhythm, normal variant and abnormal. Results at each study day will be summarized using frequency tables. Any changes after injection from baseline will be summarized using shift tables and subjects with abnormal ECG results after dosing will be identified using listings.

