7.4. Electrocardiogram

A 12-lead ECG will be performed at screening and reviewed by the study PI or a co-Investigator to assess the cardiac status of a subject for eligibility for enrollment. ECGs will be performed after the subject rests quietly in a supine position for at least 10 minutes. To be eligible for participation, the QT interval should be \leq 450ms, and there must be no clinically significant ECG abnormalities according to the study investigators and may be repeated once. A 12-lead ECG will also be performed after a subject has been dosed.

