7.0 Statistical Methods

General statistical conventions

All statistical procedures will be completed using SAS version 9.4 (or higher), R version 4.0.0 (or higher), or Phoenix WinNonLin 8.3.1 (or higher).

Unless otherwise stated, all statistical testing will be two-sided and will be performed using a significance (alpha) of 0.05. Two-sided 95% confidence intervals (CI) will be provided when relevant.

Continuous variables will be summarized using descriptive statistics, including number of subjects (n), mean, median, standard deviation (SD), interquartile ranges (IQR), minimum, and maximum.

For categorical variables, summaries will include counts of subjects and percentages. Percentages will be rounded to one decimal place.

For summary purposes, baseline will be defined as the last available pre-dose value. All summaries will be presented by treatment group, unless otherwise specified.

All subject data, including those derived, will be presented in individual subject data listings. Unless otherwise stated, unscheduled visit results will be included in date/time chronological order, within patient listings only. All listings will be sorted by subject ID, date/time and visit. The treatment group will be stated on each listing. Unless otherwise stated, data listings will be based on FAS.

Unscheduled data points will not be used in any summary tables separated by visit but will be presented in each listing as appropriate.

Subject disposition

Subject disposition information will be summarized by dosing cohort, treatment group and overall. The number and percentage of subjects who are enrolled, who complete the study, and who withdraw early from the study will be presented.

The primary reasons for early withdrawal will also be tabulated, including withdrawal by subject, physician decision, lost to follow-up, major protocol deviation or other.

The number of subjects enrolled will be used as the denominator for the percentage calculation. Subject disposition will be listed.

The number and percent of subjects in each analysis set will also be tabulated. A listing of each subject excluded from an analysis population will be listed as well as the reason why they were excluded from the population.

Treatment Misallocations: if a subject is

- Randomized but withdrawn prior to dosing, then they will be replaced and will not be included in any analysis.
- Randomized but receive incorrect treatment, they will be reported under the treatment they actually

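### SAP 8.7.5 measures PR, QRS and QTcF but tabulates only a three-level ECG reading, so an interval shift within one category appears in no specified table

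*SAP*

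**What the plan says.** SAP 8.7.5 schedules a 12-lead ECG at screening and another on the dosing day, 30±10 minutes after injection, on a machine that "automatically calculates the heart rate and measures PR, QRS, and QT (QTcF), intervals". Protocol 7.4 uses the screening tracing for eligibility and adds that "A 12-lead ECG will also be performed after a subject has been dosed".

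For analysis, SAP 8.7.5 then says "Results will be categorized as normal sinus rhythm, normal variant and abnormal. Results at each study day will be summarized using frequency tables". For change it says "Any changes after injection from baseline will be summarized using shift tables and subjects with abnormal ECG results after dosing will be identified using listings". It gives no cut-points for the three categories and mentions no numeric summary of an interval. SAP 8.4.2 likewise places baseline ECG results among the categorical characteristics.

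The general conventions in SAP 7.0 state that "Continuous variables will be summarized using descriptive statistics, including number of subjects (n), mean, median, standard deviation (SD), interquartile ranges (IQR), minimum, and maximum" and that all subject data will be listed. They do not mention ECG intervals.

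**The concern.** Each subject should have a numeric PR, QRS and QTcF before and after dosing, yet the section that governs ECG analysis replaces these with one overall reading. Protocol 5.2 excludes subjects with marked QT/QTc prolongation or a clinically significant abnormal ECG, so most subjects will start outside the abnormal category and have room to move without changing category.

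A modest, consistent lengthening of an interval in a dose cohort could then leave the frequency and shift tables unchanged. A reader of the report would have to rebuild the mean change from individual listings. In a first-in-human study whose primary objective is safety and tolerability, these paired tracings are the only scheduled information on cardiac intervals. Summarising them takes little work.

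**Working it through.** **Step 1. How each safety measurement is summarised.**

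| Measurement | Where | Specified summary |
|---|---|---|
| Laboratory values | SAP 8.7.2 | Visit value and change from baseline, descriptive statistics; abnormal results by severity |
| Vital signs, including heart rate | SAP 8.7.3 | Visit value and change from baseline at each visit or timepoint, descriptive statistics |
| PR, QRS, QTcF | SAP 8.7.5 | None numeric; one overall three-level reading in frequency and shift tables, and a listing of abnormal post-dose results |

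Protocol 11.3.3.2 asks for change from baseline in vital signs, physical examinations and laboratory values and does not name ECG. SAP 8.7.5 is therefore the only text that sets the ECG analysis.

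**Step 2. What the specified ECG tables can show.** A move between any two of the three categories appears in the shift table. A change in PR, QRS or QTcF within one category does not. The values themselves stay in the listings under SAP 7.0.

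**Step 3. What an unchanged shift table would mean in one cohort.** The plan states no ECG figure. Its only precision figures (SAP 4.0, Protocol 11.1) concern event proportions in 8 active subjects, and they reproduce:
- P(at least one event) = 1 − (1 − p)^8, which is 1 − 0.85^8 = 0.728 at p = 0.15 and 1 − 0.5^8 = 0.996 at p = 0.5.
- Upper exact 95% bound with 0 of 8 = 1 − 0.025^(1/8) = 0.369.

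By the same bound, if none of 8 subjects changes category, the true proportion who would change could still be as high as 0.369. This holds wherever the category boundaries lie.

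**Step 4. What the numeric summary would add.** The documents give no SD for the change in QTcF, so 8 to 15 ms is an assumption. The 95% half-width for a mean change is t(0.975, n − 1) × SD / √n.
- One active cohort, n = 8, t = 2.365: 2.365 × 8 / √8 = 6.7 ms, and 2.365 × 15 / √8 = 12.5 ms.
- Pooled placebo, n = 5 × 2 = 10, t = 2.262: 2.262 × 8 / √10 = 5.7 ms, and 2.262 × 15 / √10 = 10.7 ms.

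The table would give an estimate with stated precision, though not a tight one at this sample size.

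**The case against.** The best defence is that SAP 7.0 already promises descriptive statistics for continuous variables and that the table shells are in a separate document (SAP 1.0), so an interval table may already be planned. That possibility stands, but it does not settle the matter. SAP 8.7.5 is specific to ECG and names only categorical output, and SAP 8.4.2 does the same at baseline. Chemistry and hematology also appear in that categorical list, yet SAP 8.7.2 goes on to specify value and change for them; SAP 8.7.5 has no matching sentence. A programmer following the text would produce no interval table.

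Several limits stand in full:
- ECG change is not among the primary endpoints (Protocol 3.2.1), so treating it differently from vital signs and laboratory values fits the endpoint list.
- There is one post-dose tracing, and it precedes the first post-dose PK sample at 2 hours (Protocol 8.2).
- The baseline tracing is taken at screening, Day -14 to Day -2, with no time-matching specified.
- The documents reviewed identify no QT signal.

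A reader might also infer that heart rate goes untabulated. It does not: SAP 8.7.3 summarises vital-sign heart rate with change from baseline, and Protocol 8.2 measures it 15 minutes after injection, hourly for 2 hours, then every 2 hours for 4 hours. Only the duplicate ECG-derived value lacks a table.

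A reader might infer that the tables detect only a crossing into the abnormal category. That is too strong, because a move from normal sinus rhythm to normal variant would also show.

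**Conclusion.** The point holds for PR, QRS and QTcF. They are measured, but the SAP text specifies no numeric table for them, so a within-category shift would be found only in listings. It is a shortfall in summarising, not a loss of data, and it leaves no named endpoint unanalysed.

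The size is modest. It concerns three intervals with one screening and one post-dose value per subject, and a cohort mean change would be known to about ±6.7 to ±12.5 ms under the assumed SD of 8 to 15 ms. It would be tempting to express the benefit as a gain in power over the category table. The documents do not support such a figure: they give no mean or SD for QTcF and no expected shift, they never define abnormal by a QTcF value, and SAP section 8 plans no statistical tests on safety endpoints.

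The conclusion assumes that the machine's interval values are, or can be, captured for analysis, and that the unseen shells follow the SAP text.

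**What to change.** In SAP 8.7.5, add a descriptive summary of PR, QRS and QTcF showing the screening value, the post-dose value and the change from baseline, with the mean change and its two-sided 95% CI, by dose cohort and pooled placebo. Keep the three-category frequency and shift tables and the listing. State how the three categories are assigned, since the section does not say.

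The cost is one paragraph and one table. The measurements already come from the machine, so no visit or procedure changes. The one possible extra task is transferring the interval values into the analysis data if the eCRF holds only the overall reading. If the shells already contain such a table, the change is a sentence in SAP 8.7.5 that says so.

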8.7.6 Other safety assessments

A hypersensitivity panel includes cytokine and complement panels, IgE and tryptase. A blood sample will be drawn prior to dosing and additional two blood samples will be drawn during and after the event if a subject develops anaphylaxis or anaphylactoid reaction. The samples will only be processed if the subject has a hypersensitivity reaction. Subjects with hypersensitivity reaction will be identified using listings and summarized descriptively by treatment group.

A nasopharyngeal swab specimen will be collected for RT-PCR testing for SARS-CoV-2 at screening and upon presentation of COVID-19 symptoms. Subjects with positive testing results will be identified using listings and summarized descriptively by treatment group.

8.8.1 Subgroup analysis

No planned subgroup analysis will be conducted.

8.8.2 PK analysis

PK parameters will be estimated for total antibodies of ADM03820 as measured by ELISA for samples from Cohorts 1 and 2. PK parameters for each monoclonal antibodies of ADM03820 as measured by ELISA for

samples from Cohorts 3-4 using noncompartmental methods. All analysis will be conducted in WinNonlin or a similar software package. Parameters will be estimated by dose cohort. Summary statistics will include the mean, median, coefficient of variation, and range. When evaluable, estimated PK parameters will include:

- AUC_(0-t): Area under the concentration time-curve to the last concentration above the lower limit of quantitation
- C_{max}: Maximum observed concentration
- T_{max}: Time of maximum observed concentration
- λ_z: Elimination rate constant
- AUC_(0-∞): Area under the concentration time-curve extrapolated to infinity
- t_{1/2}: Terminal elimination half-life
- CL: Total clearance
- Vz: Volume of distribution

Additionally, multi-compartmental models will be considered based on inspection of concentration-time curves. If models are fit, base models will assume first-order elimination from the central compartment, and models will be parameterized in terms of clearance, volume of distribution and inter-compartmental rates. Standard objective goodness of fit measures will be used to determine the final model.

Interim analysis (IA)

Two blinded interim analyses are planned for this study. See Table 4 below for their schedule and scope. No adjustment for multiplicity will be made at these interim analyses.

Table 4: Schedule and scope of IAs

IA Number	Time	Cohorts	Scope	
1	Day 30	Cohorts 1 and 2	Safety, PK	
2	Day 60	Cohorts 1-3	PK	
3	Day 60	Cohort 5	Safety, PK	
4	Day 90	Cohort 1-4	Safety	

Refer to Section 8.6.5 and Section 8.8.2 for analysis methods. An interim CSR will be generated after all subjects complete Day 90.

8.0 Changes to Planned Analysis from Study Protocol

Added per-protocol population in protocol section 11.3.1.

Resilience Government Services, ADM03820-001

BST1302-SOP-T01/v1.0/2020 Page 25 of 26

10.0 Appendices

None.
